The Comprehensive® Shoulder System with nano humeral component addresses these issues by offering a minimally invasive humeral component that allows the surgeon to recreate the patient's natural humeral head version and inclination, while also allowing unobstructed access to the glenoid. The Comprehensive® Shoulder System with nano humeral component is an evolved design based on the Biomet TESS® shoulder that is currently marketed outside of the United States including Europe and Canada. The Comprehensive® Shoulder System with nano humeral component has a reverse morse taper locking mechanism that allows it to interface with Biomet's current offering of Comprehensive® shoulder components for enhanced flexibility in the surgical suite. The Comprehensive® nano also utilizes Biomet's proven PPS® Porous Plasma Spray technology for proximal fixation.

SECTION A: PURPOSE PURPOSE/OBJECTIVES

The purpose of this clinical investigation is to establish the safety and efficacy of the Comprehensive® Shoulder System with nano humeral component in Total Shoulder Arthroplasty. Safety and efficacy of the device will be measured by collection and analysis of the following data at the two-year or greater time point (22 months post-operative or longer):

- 1. American Shoulder and Elbow Surgeons (ASES) Score
- 2. Single Assessment Numeric Evaluation (SANE)
- 3. Constant Score
- 4. Radiographic assessment of osteolysis, radiolucencies, migration, and subsidence
- 5. Comparison of overall adverse event rates including rates of removal/revision and other serious adverse events.

Please refer to the Statistical Analysis Section for a description of the analyses that will be used.

RATIONALE FOR CURRENT STUDY

The current study is designed to determine the safety and efficacy of the Comprehensive[®] Shoulder System with nano humeral component implants (investigational) by measuring clinical, radiographic and safety outcomes when compared to the Comprehensive[®] Shoulder System with mini stem component (control) at the two-year or later follow-up time point.

The data collected as part of this study will be used to support Pre-Market Notification (U.S.) clearance of the Comprehensive[®] nano Humeral shoulder system and as such will be conducted according to all relevant FDA regulations for IDE clinical trials, sponsor and IRB requirements.

SECTION B: PROTOCOL OVERALL DESIGN

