It is possible that during the course of the study, certain changes may become desirable, although none are anticipated at this time. All changes to the investigation require prior approval from the investigator's Institutional Review Board (IRB) or Ethics Committee (EC) and if necessary, the FDA. Any other deviation from the stated protocol will be considered as such and will be reported accordingly. Since TSA is an elective procedure, it is not expected that treatment will require administration in an emergency setting, therefore all changes to the protocol require review and approval by the investigator's IRB prior to implementation.

RADIOGRAPHIC PROTOCOL

A detailed radiographic protocol is contained in Exhibit 3.

STATISTICAL ANALYSIS PLAN

This is a two-group, multi-center, randomized single blinded clinical trial to compare Total Shoulder Arthroplasty with Biomet's Comprehensive[®] Shoulder System with nano humeral component to another active intervention, a Total Shoulder Arthroplasty with Comprehensive[®] Shoulder System with mini stem component (abbreviations: Investigational vs. Control).

PRIMARY STATISTICAL HYPOTHESES AND DEFINITION OF STUDY SUCCESS

This study is designed to show that the Investigational device is non-inferior to the control device using three co-primary study endpoints. This will be shown using a closed testing method in which each of the primary endpoints specified below are compared using α =0.05. Study success requires that the Investigational group successfully demonstrate non-inferiority when compared to the Control group for all three of the individual primary endpoints, using the statistical methods described below. Because non-inferiority must be successfully shown for all three endpoints for study success, the type I error rate is preserved at 5% for the entire primary endpoint.¹

The individual non-inferiority hypotheses for each of these three tests are as follows:

Radiographic Success

The proportion of successful outcomes (i.e., patients meeting radiographic success criteria) in the Investigational group is non-inferior to the proportion of successful outcomes in the Control group using a 10% margin of non-inferiority. The test is based on the lower bound of a one-sided 95% confidence interval for the difference, Investigational minus Control, in proportions of success at 22+ months. A conclusion of non-inferiority is supported if the lower bound of the confidence interval is at least -0.10.

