Theoretically Due: The number of implants that could be examined if all subjects returned on the first day of the follow-up window based on their respective initial surgery dates and the date of database closure.

Deaths: The number of deaths that have taken place in the course of the investigation according to scheduled follow-up visits.

Revisions: The number of revisions that have taken place in the course of the investigational study recorded according to the scheduled follow-up visit.

Withdrawal of Consent: The number of subjects that have withdrawn during the course of the investigational study recorded according to the scheduled follow-up visit.

Not Yet Overdue: Subjects in this category are those who have not yet been evaluated but who are still within the evaluation time window at the time of database closure.

Actual^A: The number of subjects with complete data (i.e. all primary outcomes can be determined) who are actually evaluated within the protocol-defined follow-up intervals.

Actual^B: The number of subjects with any follow-up data (in- or out-of-window) reviewed or evaluated by investigator ("all evaluated" accounting).

Expected: This element is the number of subjects expected for a given time interval. These include the theoretical number of subjects who are due to be evaluated, less the number of subjects who have died, withdrawn, been revised, or are not yet overdue in this time interval.

Follow-up Rate: This element is the ratio of actual subjects evaluated to expected subjects, expressed as a percentage.

MODELS FOR CONTINUOUS MEASURES

Comparisons of Investigational vs Control with regard to continuous baseline and secondary outcomes will be performed using standard statistical tests and will be chosen as appropriate for the scale and distribution of the measures being analyzed. A t-test, Wilcoxon test, or oneway ANOVA (as appropriate) will be performed to assess differences.

CATEGORICAL DATA ANALYSES

Comparisons of Investigational vs Control with regard to categorical baseline, secondary and safety outcomes will be performed using standard statistical tests and will be chosen as appropriate for the scale and distribution of the measures being analyzed. Specifically, categorical outcomes will be compared for investigational and control groups using the Fisher's Exact test (for 2x2 tables) or the Likelihood Ratio chi-square test (for tables larger than 2x2).

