BASELINE CHARACTERISTICS

Subjects in the Investigational and Control study groups will be compared regarding a list of baseline items, including preoperative ASES and Constant Scores, demographics (age, gender, and primary diagnosis), medical history, and comorbidities.

EFFICACY EVALUATIONS

Primary Endpoint

The confidence intervals used in the analysis of the binary primary endpoints (Radiographic Success and Absence of Revision/Removal/UADE) will be 1-sided, 95% confidence intervals for the difference between proportions in two independent samples. They will be calculated using the Wald method as based on a normal approximation to the binomial, as follows:

$$(p_C - p_I) + z_\alpha \sqrt{SE_C^2 + SE_I^2}$$

Where

 p_{C} = proportion of success in the Control group, p_{I} = proportion of success in the Investigational group, α = 0.05, and

$$SE_C = \sqrt{\frac{p_C(1-p_C)}{n_C}}$$
 and $SE_I = \sqrt{\frac{p_I(1-p_I)}{n_I}}$

The confidence interval used in the analysis of the continuous primary endpoint (ASES Score) will be a 95% confidence interval for the difference between means in two independent samples. They will be calculated using the normal distribution, as follows:

$$(\overline{x}_C - \overline{x}_I) + z_\alpha \sqrt{\frac{s_C^2}{n_C} + \frac{s_I^2}{n_I}}$$

Where

 x_{C} = mean ASES score in the Control group,

 $\overline{x_{I}}$ = mean ASES score in the Investigational group,

 $s_{\scriptscriptstyle C}$ = standard deviation of the ASES scores for the Control group,

 s_{T} = standard deviation of the ASES scores for the Investigational group, and

 $\alpha = 0.05$

Secondary Endpoints

Secondary outcomes include the ASES score, SANE score, Constant score, and radiographic endpoints at 6 weeks, 6 months, 1 year, and 2 years separately. These outcomes will be compared for Investigational and Control groups at each time point.

Exploratory Analyses14

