There is no gender selection criteria prescribed for this investigation. Male and female subject candidates will be solicited for participation in the investigation without bias. The proportion of male to female subjects will be examined to assure that there is no difference between control and investigational groups with respect to this ratio. If an unexpected difference in this ratio exists between control and investigational groups, then a covariate analysis controlling for gender will be performed for the primary analysis of the investigation. This will assure that gender related effects, if they are present, do not bias investigation conclusions.

Conclusion

This clinical investigation will be conducted under a well-defined protocol and subjects will be informed of the potential risks, benefits, and alternate treatments available prior to giving their consent for participation as investigational subjects. Exposure to the investigational device will be determined at random. Subjects' clinical course will be closely monitored and reported on throughout the investigation and new information provided to them that could affect their willingness to participate. The investigational device that will still allow for a valid, scientific analysis of the reported data. The reporting and assessment of all untoward events arising during the course of the investigation will also be required. Therefore, the sponsor believes that all risks that are reasonably foreseeable have been identified and the means for adequately controlling those risks described.

SECTION D: DEVICE DESCRIPTION DEVICE DESIGN AND DESCRIPTION

The Comprehensive[®] Shoulder System with nano humeral component is a humeral prosthesis system intended for use in shoulder replacement surgery. The implant can be utilized for primary shoulder replacement in conjunction with the 510(k) cleared Versa-Dial[™] Humeral Heads (K040610, K060716) and Comprehensive[®] Hybrid Glenoids (K060694). A complete component listing is included in Exhibit 12.

INVESTIGATIONAL DEVICE DESCRIPTION

The subject of this clinical investigation is the Comprehensive[®] Shoulder System with nano humeral component, comprised of the following components:

- A porous-coated stemless humeral component for cementless fixation;
- A polished, modular (2-piece) humeral head for articulation with the glenoid component;
- A molded glenoid component with three peripheral pegs for cemented fixation;

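### The primary ASES interval could pre-specify adjustment for pre-operative ASES and site at almost no cost, and the gender-adjustment rule in Section C should be reconciled with the SAP in the same amendment

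*Combined protocol and SAP*

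**What the plan says.** **ASES analysis.** Under Efficacy Evaluations, Primary Endpoint, the ASES interval "will be a 95% confidence interval for the difference between means in two independent samples". It uses the two sample means, the two sample variances and a normal quantile. Primary Statistical Hypotheses compares the one-sided 95% lower bound (Investigational minus Control) with -9.5 points.

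**Where baseline and site appear.** The Randomization section lists the pre-operative ASES score among the papers that the sponsor reviews before enrolment, Table 1 schedules it, and a score of 40 or below is an entry criterion. Randomization Details blocks by site with a separate plan for each. In the analysis, pre-operative ASES enters only the baseline comparison and the exploratory analyses. Site enters the interaction tests (with a possible stratified consistency check) and the protocol-deviation comparison.

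**Gender.** Section C, Description of Subject Population, compares the proportion of men to women between the arms and makes an imbalance the trigger: "If an unexpected difference in this ratio exists between control and investigational groups". No test or threshold is attached to that condition. The stated consequence is that "a covariate analysis controlling for gender will be performed for the primary analysis of the investigation". No model or effect scale is attached to that either.

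**What decides success.** The SAP requires non-inferiority "for all three of the individual primary endpoints, using the statistical methods described below". Those methods are the unadjusted ASES interval and, for the binary endpoints, one-sided "95% confidence intervals for the difference between proportions in two independent samples". Section A also sends the reader to the statistical section: "Please refer to the Statistical Analysis Section for a description of the analyses that will be used".

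**The concern.** A baseline value of the outcome and the blocking factor of the randomisation are the two covariates one would normally consider for a continuous primary endpoint. Leaving them out gives up whatever precision they offer. It also leaves the analysis out of step with a design balanced within site: if site is prognostic, the unadjusted standard error is somewhat too large. What is at stake is a modest amount of power on one of three endpoints that must all pass.

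The gender sentence raises a separate, smaller question. It ties an adjusted analysis to the primary analysis, but does not say when it starts, how it is done for endpoints judged on a risk-difference margin, or whether it bears on study success.

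**Working it through.** **Inputs from the documents:** SD 19, ASES margin 9.5, one-sided α 0.05, power 0.90, radiographic success 0.93 with margin 0.10, 15% attrition, 132 per arm, at most 17 sites. Shoulders are treated as independent, as in the plan.

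**Assumptions (not in the documents):** baseline-to-outcome correlation r, share of variance due to site, share of women, size of any gender effect.

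**1. The plan's own figures reproduce.**
- ASES: n = 2σ²(z₀.₉₅ + z₀.₉₀)²/δ² = 2 × 361 × 8.564/90.25 = 68.5, so 69 by the normal formula. The noncentral-t version gives 70, the plan's figure.
- Radiographic: 2 × 0.93 × 0.07 × 8.564/0.01 = 111.5, so 112. Then 112/0.85 = 131.8, so 132 per arm.

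**2. Unadjusted ASES at 112 per arm.**
- SE = 19√(2/112) = 2.539, and half-width = 1.645 × 2.539 = 4.18.
- Power at no difference: Φ(9.5/2.539 − 1.645) = 0.98.
- Power at -3: Φ(6.5/2.539 − 1.645) = Φ(0.915) = 0.82.

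**3. Adjusting for baseline alone.** The SD becomes 19√(1 − r²).

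| r | SD | SE | Half-width | Power at -3 |
|---|---|---|---|---|
| 0 | 19.00 | 2.539 | 4.18 | 0.82 |
| 0.1 | 18.90 | 2.526 | 4.16 | 0.82 |
| 0.2 | 18.62 | 2.488 | 4.09 | 0.83 |
| 0.3 | 18.12 | 2.422 | 3.98 | 0.85 |

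**4. Baseline and site together**, simulated: 264 shoulders, 17 sites, blocks of 4 (assumed), 224 retained at random, HC2 standard error, t quantile, 3,000 runs per setting.

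| r | Half-width, site not prognostic | Half-width, site 5% of variance |
|---|---|---|
| 0 | 4.21 | 4.12 |
| 0.1 | 4.20 | 4.11 |
| 0.2 | 4.14 | 4.04 |
| 0.3 | 4.02 | 3.93 |

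With nothing prognostic the bound widens by 4.21 − 4.18 = 0.03, or by 4.22 − 4.17 = 0.05 in a separate run with 17 equal sites. At r = 0.3 it narrows by 0.16 to 0.25. Power at -3 is 0.815 (r = 0), 0.826 (0.2) and 0.845 (0.3) with no site effect, and 0.859 at r = 0.3 with the 5% share. Type I error at -9.5 (6,000 runs per setting) is 0.047–0.056 unadjusted and 0.045–0.053 adjusted.

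**5. The gender trigger.** Exact enumeration of two Binomial(132, 0.5) counts gives the chance that each reading fires under randomisation alone:

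| Reading of the trigger | Fires in |
|---|---|
| Fisher p<0.05 | 4.2% of trials |
| Fisher p<0.10 | 7.4% |
| Gap of 10 points or more | 9.6% |
| Gap of 5 points or more | 42% |
| Any gap | 95% |

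**6. Type I error for ASES at -9.5**, simulated with 100,000 runs per setting and 112 of 132 per arm analysed, for assumed gender effects of 0/5/10 points:
- SAP interval alone: 0.0512/0.0505/0.0499.
- Better bound chosen only when Fisher p<0.05: 0.0514/0.0510/0.0507, an increase of 0.0002/0.0005/0.0008.
- Better bound chosen in every trial: 0.052–0.054, 0.056–0.057 and 0.060–0.062 across separate simulations.

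Under a fixed Fisher rule, with the adjusted bound deciding whenever the trigger fires, the rate is 0.050–0.052. For radiographic success at 0.93 against 0.83, the Wald bound alone gives 0.056 and the fixed rule 0.055–0.056.

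**The case against.** **On adjustment.** The unadjusted interval is unbiased and, if site matters, conservative. ASES power is already 0.98 at no difference, and radiographic success, not ASES, sets the sample size. The ASES entry limit of 40 restricts the baseline range and probably weakens the correlation. Adjustment brings up to 16 site degrees of freedom and a pooling rule, and the bound can widen slightly. The SAP already provides a site check. All of this stands. It is why the point is an improvement with a modest, assumption-dependent gain. A reader might infer that omitting baseline and site biases the result or invalidates the test; neither the documents nor the calculations support that.

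**On gender.** A reader might infer that the plan has two competing primary analyses, that nobody can say which decides success, and that type I error is materially inflated. The documents do not support this. The SAP defines success by its own methods and gives the formulas. The gender sentence sits in the risk section, says only that an analysis will be performed, and attaches no decision rule. Exploratory Analyses already plans regressions of each primary endpoint that include gender, and Significance Levels bars exploratory results from claims of significance. The nearest documented trigger is Fisher's exact test: Baseline Characteristics lists "demographics (age, gender, and primary diagnosis" among the comparisons, and Categorical Data Analyses says: "Specifically, categorical outcomes will be compared for investigational and control groups using the Fisher's Exact test (for 2x2 tables". No section links that test to the gender rule or sets a level for baseline comparisons. What remains is missing clarity on trigger, scale and rank. The planned logistic model also gives an odds ratio, which cannot be read directly against a margin of -0.10.

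**Conclusion.** The ASES point holds as a cheap improvement. Adjusting for baseline alone reduces the half-width by 0.09 points at a correlation of 0.2 and by 0.20 at 0.3, raising power at a true difference of -3 by about 0.01 and 0.03. With site in the model, the change runs from 0.05 points wider (nothing prognostic) to 0.25 narrower (correlation 0.3, site share 5%). All of this rests on an assumed correlation and site share, with 112 shoulders per arm and SD 19. The sample size is not in question.

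The gender point is real but minor. Under a fixed rule type I error stays at about 0.05. With a Fisher p<0.05 trigger, even choosing the better ASES bound adds less than about 0.001. It reaches about 0.06 only if the better bound may be chosen in every trial, balanced or not, and gender has a large effect; the 10 points assumed there exceeds the 9.5-point margin.

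**What to change.** **ASES.** Pre-specify the primary analysis as a linear model of 22+ month ASES on treatment, pre-operative ASES and site, with a standard error that allows unequal variances (for example HC2). Compare the one-sided 95% lower bound, Investigational minus Control, with -9.5. Pool small sites by the rule already given under Protocol Deviations (three or fewer cases in either arm), and merge the pooled site with the smallest remaining site if it still falls under that limit. Keep the present interval as a sensitivity analysis.

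**Gender.** Delete the triggered adjustment in Section C. Alternatively, state that a gender-adjusted analysis of each co-primary endpoint is always run as a sensitivity analysis (linear model for ASES; gender-stratified Mantel-Haenszel risk difference for the binary endpoints, on the -0.10 scale), and that study success rests only on the primary bounds in the SAP.

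**Cost.** One amendment, with IRB approval and FDA approval where applicable, made before outcomes by arm are known. It needs no new data and no change of margin, outcome or sample size. The price is the extra model detail, up to 16 site degrees of freedom, and a bound about 0.03 to 0.05 points wider if neither covariate is prognostic. If the sponsor prefers the simpler ASES interval, the gender clarification can be made on its own.
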